9.1.2. Screening Phase

The procedures specified in the [Time and Events Schedule](#) will only be performed after written informed consent has been obtained. Screening may be conducted in part via a sponsor- and

Independent Ethics Committee (IEC)/Institutional Review Board (IRB)-pre-approved non-study specific screening consent process, but only if these pre-screening procedures are identical to the per protocol screening tests and are within the 48 hours window prior to screening completion. However, no study specific procedures, other than screening assessments, will be performed until the subject has signed the study-specific ICF. The non-study specific ICF will be considered source data.

Screening should be completed as soon as possible and the subject will be randomized within 5 days of RSV symptom onset to ensure the eligibility of the subject. Procedures that are standard of care and performed within approximately 48 hours prior to randomization may be used in determining study eligibility or determining baseline values. The results of the safety laboratory tests performed at the local laboratory must be in accordance with Section 4. The investigator may consider the subject eligible if the previously abnormal laboratory test result is within normal range on a repeat testing in the local laboratory. Repeat testing is only allowed once.

During screening 1 mid-turbinate nasal swab (if non-intubated) or 1 endotracheal sample (if intubated) will be collected and aliquoted for:

- RSV diagnosis using a PCR-based assay (at the local laboratory).
- RSV diagnosis confirmation using a PCR-based assay (at the central laboratory).
- Examination of viral and bacterial co-infection using multiplex PCR (at the central laboratory).
- Leftover mid-turbinate nasal swabs will be stored and may be used for biomarker research if warranted. Details on the purpose of the biomarker research are described in Section 9.5.

9.1.3. Double-blind Treatment Phase

Assessments to be performed during the treatment phase are specified in the [Time and Events Schedule](#).

Day 1/Day of Randomization

Eligible subjects will be randomized on Day 1. Study drug administration should start as soon as possible, but no later than 4 hours after randomization. Subjects will be dosed with a single oral LD on Day 1. Depending on the time of screening/enrollment, subjects will receive the first MD of study drug on Day 1. Subjects will receive no more than 2 doses per calendar day.

Assessments to be performed on Day 1 are specified in the [Time and Events Schedule](#). The local nasal swab sample can be used as the screening sample for the study if it fulfills the sample requirements for nasal swabs collected for study assessments. If the local sample or screening sample was taken less than 8 hours prior to the administration of the LD, the predose sample assessment (Day 1 swab) does not need to be performed. The mid-turbinate nasal swab (if non-intubated) or the mid-turbinate nasal swab and endotracheal sample (if intubated) should be taken as close as possible to and before the LD on Day 1. The timing of the LD will determine the timing of the nasal swab and endotracheal sample (if intubated). If the LD is in the morning,

all samples will be taken before the morning dose; if LD is in the afternoon, all samples will be taken before the afternoon doses but after the morning dose (Figure 3).

Figure 3: Two Scenarios for the Timing of Collection of Nasal Swabs and Endotracheal Samples (if Intubated)

Green dots represent study drug administration.

Red stars represent collection of nasal swab, and of endotracheal sample, if intubated.

Day 2 to Day 5/6 (End of Treatment)

Study drug administration continues until 10 doses have been taken. Subjects will receive 9 MDs without regard to food intake twice daily (at least 8 hours apart and maximum 16 hours apart, with no more than 2 doses per calendar day) through Day 5/6 (depending on the timing of the LD administration). The date and time of dose administration, the date and time of food intake (limited to the food ingested within 30 minutes before or after study drug administration), and the type of food will be recorded in the eCRF during hospitalization. The subject may be discharged after Day 2 following completion of study procedures. Subjects may also remain hospitalized if warranted by the subject's clinical status. In case the subject is discharged prior to the completion of treatment, study drug will continue to be administered at home by the subject until all doses are administered (Day 5/6), and the date and time of dose administration will be recorded in the electronic device used for eCOA. Instructions will be given to the subject regarding drug administration by the investigator or a qualified member of the study-site personnel.

Assessments will be performed as detailed in the [Time and Events Schedule](#). The eCOA (investigator and subject questionnaires) and the mid-turbinate nasal swabs (if non-intubated) (from the same nostril throughout the study) or the mid-turbinate nasal swab and endotracheal samples (if intubated) are to be taken once daily prior to study drug administration at approximately the same time each day (see [Figure 3](#)). In case of nostril bleeding or irritation during the collection of a mid-turbinate nasal swab, all subsequent nasal swabs will be performed on the contralateral nostril. Samples will be collected through Day 6 whether the subject is in hospital or has been discharged. Should the study drug duration be increased to up to 10 days (following review of the data by the IDMC), samples will be taken every day up to and including 1 day (+2 days) following the last dose of study drug. In case mid-turbinate nasal swabs are

collected at home, the subject (or the subject's spouse, partner, relative, or friend) should collect swab specimens after being trained by the investigator/study-site personnel. Subjects will be required to document the actual dates and times of collection of the nasal swab at home on the electronic device used for eCOA. Nasal swabs collected at home should be stored immediately between 2°C and 8°C (in the refrigerator) and brought to the site at the next visit.

Hospitalization duration will not be extended solely for study purposes. Telephone calls to the subjects to facilitate compliance with study procedures between outpatient study visits are permitted.

9.1.4. Posttreatment Phase (Follow-up)

Days 7 to 28

Subjects will be evaluated for a total of 28 days after randomization. If they are not hospitalized they will be required to return to the hospital for follow-up assessments as an outpatient on Day 7, Day 10, Day 14, and Day 28 as indicated in the [Time and Events Schedule](#). On Day 28 all subjects will complete the study either as an inpatient or outpatient.

Should the study drug duration be increased to up to 10 days (following review of the data by the IDMC, refer to Section [11.12](#)), additional study drug may be provided, if needed.

If a subject is discontinued from study drug, a follow-up visit will be scheduled 2 days (+2 days), 5 days (+2 days), 9 days (+2 days), and 23 days (±2 days) after the last dose of study drug was administered. Assessments should be performed as indicated in the [Time and Events Schedule](#), respectively for the Day 7, Day 10, Day 14, and Day 28 visits.

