Blood sampling for pharmacokinetics ^w		X	X	X	X			X				
Biomarkers												
Blood sampling for biomarkers (host RNA)	X	X	X		X					X		
Ongoing Subject Review												
Concomitant therapy ^x	X	X	X	X	X	X	X	X	X	X	X	X
Adverse events ^y	X	X	X	X	X	X	X	X	X	X	X	X

Abbreviations: ADL: Activities of Daily Living; AE: adverse event; bid: twice daily; CPE: complete physical examination; DBP: diastolic blood pressure; DLCO: diffusing capacity of the lung for carbon monoxide; DPE: directed physical examination; ECG: electrocardiogram; eCOA: electronic Clinical Outcome Assessment; eCRF: electronic case report form; EoS: end of study; EQ-5D-5L: EuroQol 5 Dimension 5 level version; HRQoL: health-related quality of life; ICF: informed consent form; IDMC: Independent Data Monitoring Committee; LD: loading dose; MD: maintenance dose; PK: pharmacokinetic(s); Q4h: every 4 hours; Q8h: every 8 hours; RI-PRO: respiratory infection patient-reported outcome; RNA: ribonucleic acid; RSV: respiratory syncytial virus; SAE: serious adverse event; SBP: systolic blood pressure; SpO₂: peripheral capillary oxygen saturation.

Footnotes:

- a. If a subject is discontinued from study drug, a follow-up visit will be scheduled 2 days (+2 days), 5 days (+2 days), 9 days (+2 days), and 23 days (±2 days) after the last dose of study drug was administered. Assessments should be performed as indicated in the [Time and Events Schedule](#), respectively for the Day 7, Day 10, Day 14, and Day 28 visit.
- b. The subject may be discharged after the Day 2 study procedures. Subjects may also remain hospitalized if deemed appropriate by the investigator. Days 3 to 6 assessments are to be performed on a daily basis or as indicated only if the subject is still hospitalized with the exception of administration of study drug dose, mid-turbinate nasal swabs, and subject eCOA, which are to be continued at home. Hospitalization duration will not be extended solely for study purposes. Telephone calls to subjects to facilitate compliance with study procedures between outpatient study visits are permitted.
- c. If dose duration is increased to up to 10 days, then all assessments performed on Day 7 will again be performed 1 day (+2 days) after administration of the last MD.
- d. Assessments are to be performed once daily or as indicated only if the subject is still hospitalized.

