10.2. Discontinuation of Study Treatment/Withdrawal From the Study

Discontinuation of Study Treatment

A subject will not be automatically withdrawn from the study if he or she has to discontinue treatment before the end of the treatment regimen.

A subject's study treatment must be discontinued if:

- The subject withdraws consent.
- The investigator believes that for safety reasons or tolerability reasons (eg, AE) it is in the best interest of the subject to discontinue study treatment.
- The subject becomes pregnant.
- The subject has an eGFR ≤ 30 mL/min/1.73 m² according to the CKD-EPI equation.
- The subject experiences any of the laboratory abnormalities as specified in Section 9.7.1.

If a subject discontinues study drug before the end of the treatment phase, the subject will be encouraged to continue with end-of-treatment and follow-up assessments in accordance with the [Time and Events Schedule](#).

Withdrawal From the Study

Each subject has the right to withdraw at any time for whatever reason without affecting the right to treatment by the investigator. The investigator should make an attempt to contact the subjects who do not return for scheduled visits or follow-up. Although the subjects are not obliged to give reason(s) for withdrawing early, the investigator should make a reasonable effort to ascertain the reason(s) while fully respecting the subject's rights.

A subject will be withdrawn from the study for any of the following reasons:

- Lost to follow-up.
- Withdrawal of consent.
- Death.
- The subject is poorly compliant with study procedures, study drug administration, visits, and assessments, after evaluation and discussion between the investigator and sponsor.

- Decision by the sponsor to stop or cancel the study.
- Decision by the investigator to withdraw subjects.
- Decision by local regulatory authorities and IEC/IRB to stop or cancel the study.

If a subject withdraws from the study before the end of the treatment phase, the subject will be encouraged to continue with end-of-treatment and follow-up assessments in accordance with the [Time and Events Schedule](#).

If a subject is lost to follow-up, every reasonable effort must be made by the investigator/study-site personnel to contact the subject and determine the reason for discontinuation/withdrawal. The measures taken to follow-up must be documented.

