2.1. Visit Windows, Phase Definitions and Baseline

Figure 1: Schematic Overview of the Study

Phases will be constructed as follows:

Trial phase	Start date	End date
Screening (phase 0)	00:00 of the date of signing the informed consent form	1 minute before the first study medication intake
Treatment (phase 1)	Datetime of first study medication intake	Datetime of last study medication intake + 72 hours
Follow-up (phase 2)	End of the phase 1 +1 minute	23:59 of trial termination date (date of last contact).

The last phase, whichever it is for a subject, always ends on 23:59 of the day of trial termination (last contact).

Events will be assigned to phases based on their datetime, but seconds will be ignored overall. If the daypart of the start date of the event is present but the timepart is missing, the event will be treated as if it started at 00:00 on the day of the event. If the daypart of the end date of the event is present but the timepart is missing, the event will be treated as if it happened at 23:59 on the day of the event.

The number of days in the study (*reldy*) will be defined as:

$$reldy = visit\ day - reference\ day + 1$$

for visits on or after the reference day, and

$$reldy = visit\ day - reference\ day$$

for visits before the reference, where the reference day equals the start date of the treatment phase.

All scheduled assessments after first administration of trial medication will be used. Unscheduled assessments post-dose will not be used in descriptive statistics or any per-time point analysis, but will be used in the determination of the worst-case per treatment, and in listings as applicable.

For assessments on day 1 to 6 and for daily assessments after day 6, the numeric analysis visits (AVISITN) will be equal to the relday.

For assessments on Day 7, Day 10, Day 14 and Day 28, the following table will be used to allocate analysis time points:

Target Day	Analysis time point (numeric version)	Analysis time point	Time interval (days)
7	7	Day 7	[7,9]
10	10	Day 10	[10,12*]
14	14	Day 14	[12*,16]
28	28	Day 28	[17,+∞[
For Katz ADL, DLCO and Spirometry, vital signs and physical examination in outpatients, 12-lead ECG, Mid-tubinate nasal swabs, blood sampling for hematology and biochemistry			
* Depending on the VISIT label, subjects returning on Day 12 should be assigned to Day 10 or Day 14			

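### Subjects who stop study drug early have their Day 7/10/14/28 visits re-anchored to the last dose, so after a stop on Days 1 to 4 the visits come 4 to 1 days early and do not fit the SAP's study-day windows

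*Protocol*

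**What the plan says.** Protocol 9.1.4 first ties follow-up to randomization: "Subjects will be evaluated for a total of 28 days after randomization". Discharged subjects return on Days 7, 10, 14 and 28, and everyone is to finish the study on Day 28. The same section then gives a different clock to anyone taken off study drug. Their visits fall 2, 5, "9 days (+2 days), and 23 days (±2 days) after the last dose of study drug was administered", with the scheduled assessments done "respectively for the Day 7, Day 10, Day 14, and Day 28 visits". Footnote a of the Time and Events Schedule repeats the rule, starting "If a subject is discontinued from study drug, a follow-up visit will be scheduled 2 days (+2 days), 5 days (+2 days". Neither place says that the study-day visits are also kept. For a subject who stops early, Protocol 10.2 says that "the subject will be encouraged to continue with end-of-treatment and follow-up assessments", and it points to the same schedule.

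The SAP counts differently. Section 2.1 numbers days from first dose and states: "For assessments on Day 7, Day 10, Day 14 and Day 28, the following table will be used to allocate analysis time points". The windows are Days 7–9, 10–12, 12–16, and 17 onward. A return on Day 12 goes to Day 10 or Day 14 by its visit label. No allocation rule refers to the last dose.

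Some sampling is tied to study day alone. Protocol 9.1.3 has daily samples through Day 6, in hospital or at home. Footnote s lists swabs on Days 1 to 7, 10, 14 and 28. Neither depends on the subject still taking drug.

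**The concern.** The efficacy endpoints are defined on time since first dose or on study day, and they are analysed as randomized in the ITT-i set. For subjects who stop early, the protocol measures them on time since last dose instead. A result labelled Day 14 may then come from Day 10, and the SAP will file it under Day 10, leave a gap at Day 14, or (for a Day 12 or 13 visit) use it as a Day 14 value.

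Viral load is expected to fall over this period, so timing affects the value. The reasons for stopping in Protocol 9.7.1, 10.2 and Attachment 7 include liver enzymes, blood counts, eGFR and rash. Some of these could be drug effects, so the subjects affected need not be spread evenly over the arms. At stake are the visit-based secondary endpoints: viral load by visit, AUC to Day 10 and to Day 14, outpatient Katz ADL and SpO2, and the point at which Day 28 follow-up ends.

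**Working it through.** **Inputs.** Offsets 2 (+2), 5 (+2), 9 (+2) and 23 (±2) days (Protocol 9.1.4, footnote a). SAP windows 7–9, 10–12, 12–16 and 17 onward (SAP 2.1). Contrast weights from the code in SAP 4.2.3.2. AUC formulas and carry-forward rules from SAP 4.2.4.1, Table 1.

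**Step 1: the plan's own correspondence.** Study day = last-dose day L + offset. For L = 5: 5+2 = 7, 5+5 = 10, 5+9 = 14, 5+23 = 28. The stated match to Days 7/10/14/28 is reproduced, but only for L = 5. L = 6 gives 8/11/15/29, one day late. For earlier stops the visits are (5 − L) days early.

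**Step 2: all early stops.** Nominal study day, with the allowed range in brackets. The last column assumes visits on the nominal day and no other swab.

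| Last dose | Labelled Day 7 | Labelled Day 10 | Labelled Day 14 | Labelled Day 28 | Days early | Empty SAP slots |
|---|---|---|---|---|---|---|
| Day 1 | 3 (3–5) | 6 (6–8) | 10 (10–12) | 24 (22–26) | 4 | Day 7, Day 14 |
| Day 2 | 4 (4–6) | 7 (7–9) | 11 (11–13) | 25 (23–27) | 3 | Day 14 |
| Day 3 | 5 (5–7) | 8 (8–10) | 12 (12–14) | 26 (24–28) | 2 | Day 10 |
| Day 4 | 6 (6–8) | 9 (9–11) | 13 (13–15) | 27 (25–29) | 1 | Day 10 |
| Day 5 | 7 (7–9) | 10 (10–12) | 14 (14–16) | 28 (26–30) | 0 | none |

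**Step 3: what the visit allowance can repair.** For a Day 3 or 4 stop, late attendance can fill every slot. For a Day 1 or 2 stop, the visit labelled Day 10 ends at Day 8 or 9 and cannot reach the Day 10 window. The visit labelled Day 14 can then fill Day 10 or Day 14, but not both. One of the two stays empty unless another swab is taken. The Day 28 slot is always filled because its window opens at Day 17, so SAP summaries would not show that the visit was early.

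**Step 4: primary endpoint.** Dividing the code's coefficients by 4 gives weights of 1 for each of Days 2 to 6 and 0.5 for Day 7, a total of 5.5. The swabs on Days 2 to 6 follow study day. Only Day 7 is exposed: 0.5 / 5.5 = 9.1%.

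**Step 5: AUC to Day 14.** The last segment is (4/2)(y10 + y14), a fixed four-day width, with the last value carried forward if Day 14 is missing. Assume a steady decline of b log10 per day; the documents give no rate.

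- Day 1 stop, last swab on Day 10: excess = 2(y10 − y14) = 2 × 4b = 8b. For b = 0.1 to 0.5 this is 0.8 to 4.0 log10·days for that subject.
- Day 2 stop, last swab on Day 11 and used for both points: y10 + y14 = (y11 + b) + (y11 − 3b) = 2·y11 − 2b, so the excess is 2 × 2b = 4b, or 0.4 to 2.0.
- For scale: if one arm had 10 percentage points more Day 1 stops (assumed), its mean would rise by 0.1 × 8b = 0.08 to 0.40 log10·days.

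In the mixed model, which SAP 4.2.4.2 also applies to the Day 10 and Day 14 AUCs, nothing is carried forward. The empty slot is simply missing.

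**The case against.** The case against rests on how much is protected. A reader might infer that daily swabs stop with the drug and that the primary AUC is compromised. The documents do not support this: Protocol 9.1.3 and footnote s tie the swabs to study day, and 10.2 sends early stoppers to the schedule that contains footnote s. Read alone, footnote s would even keep the Day 7, 10 and 14 swabs in place. That last argument shows a conflict with footnote a rather than resolving it, since footnote a says when those visits' assessments are done.

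A reader might also infer that Day 28 outcomes are lost, or that follow-up ends up to six days early. The Day 28 slot is always filled. The six days compare the early edge of the window (Day 22) with nominal Day 28. Like for like, the shift is at most four days, because completers may attend from Day 26. Time-to-event endpoints use actual dates with censoring, the eCOA is daily to Day 28, and inpatient Katz and SpO2 assessments follow the hospital stay.

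Safety observation is partly covered as well. SAEs reported to the investigator within 30 days of last dose must be reported, deaths in that period count as SAEs, and subjects stopped for laboratory changes are followed to resolution or stabilization.

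Finally, the anchoring is partly deliberate. The Amendment 2 rationale says the visit 2 days after last dose was requested by health authorities, to be consistent with completers' Day 7 visit. That justifies having such a visit. It does not require the study-day efficacy assessments to be dropped.

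**Conclusion.** The inconsistency is real and limited in reach. For a last dose on Days 1 to 4, the Day 7, 10, 14 and 28 visits nominally come 4 to 1 days early. This contradicts Protocol 9.1.4's own follow-up from randomization and does not fit SAP 2.1. The slots at risk are Days 7, 10 and 14. Those gaps assume visits on the nominal day and no additional swab, and the +2 allowance closes some of them. The exposed endpoints are the visit-based secondary ones and the end of follow-up; the primary AUC is exposed only through Day 7.

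The total effect cannot be sized, because neither document gives a rate or timing of early stopping. It is tempting to conclude that the treatment comparison is biased. That would need stopping to differ by arm, which is plausible from the stopping criteria but not shown.

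**What to change.** Reconcile Protocol 9.1.4, footnote a, Protocol 10.2 and SAP 2.1 as follows:

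- State that efficacy assessments and swabs for Days 7, 10, 14 and 28 stay on study days counted from first dose for every randomized subject, whether or not drug is stopped.
- Keep the existing visit 2 (+2) days after last dose as an additional safety visit, combined with a scheduled visit when the windows overlap. The protocol already uses this pattern: under footnote c and Section 9.1.1, extended dosing adds a post-dose visit without removing one.
- Confirm in 10.2 that the study-day swabs of 9.1.3 and footnote s continue after drug is stopped.

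The cost is wording plus about one extra visit for each subject who stops early. There is a trade-off: the later visits of early stoppers would no longer match completers on time since last dose.

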9.2. Efficacy Evaluations

Viral Load Determination

As an evaluation of antiviral activity of ALS-008176, RSV RNA viral load will be measured in mid-turbinate nasal swabs (obtained from non-intubated subjects) or in mid-turbinate nasal swabs and endotracheal samples (obtained from intubated subjects or via suction through tracheostomy or other sampling methods) using qRT-PCR performed at the central laboratory. Samples for the determination of RSV viral load will be taken as specified in the [Time and Events Schedule](#) and Section [9.1.3](#).

RSV infectious viral load may be measured in mid-turbinate nasal swabs (if non-intubated) or in mid-turbinate nasal swabs and endotracheal samples (if intubated) using a quantitative culture method (plaque assay) in a selected number of subjects and samples at the sponsor's discretion.

Changes in viral load will be evaluated but will not be regarded as AEs or SAEs.

Viral L-gene Sequencing for Viral Resistance

Viral sequencing analysis will be performed by sequencing the polymerase L-gene and other regions of the RSV genome (may be performed if no mutations are seen in the L-gene) in samples taken before treatment (at baseline), during treatment, and posttreatment, to identify preexisting sequence polymorphisms and to characterize emerging RSV variants.

The L-gene will be sequenced pretreatment in all subjects and postbaseline in subjects not achieving viral suppression. The sequencing of postbaseline samples may be triggered at the discretion of the sponsor's virologist, based on the changes in RSV RNA viral load observed in each individual subject and the limits of the sequencing assay. The impact of newly identified mutations on in vitro antiviral activity of ALS-008176 or other RSV molecules may be assessed in in vitro studies.

Other regions of the RSV genome may also be sequenced at the sponsor's discretion.

Changes in the viral sequence will be evaluated but will not be regarded as AEs or SAEs.

Clinical Course of RSV Infection

The study will include the following evaluations of the clinical course of RSV infection:

- Clinical evaluation including, but not limited to:
 - Oxygen requirement type (eg, supplemental oxygen, noninvasive positive pressure ventilation, endotracheal-mechanical ventilation, mechanical ventilation by tracheostomy), duration, and amount.
 - Body weight.
 - Respiratory rate, heart rate, systolic blood pressure (SBP), diastolic blood pressure (DBP), and body temperature (method should be noted in the eCRF).
 - SpO₂.
 - Level of hospital care (eg, ICU, transitional care unit, ward floor).
 - Duration of hospitalization.
 - Need for hydration, and feeding by IV catheter/nasogastric tube.
 - Functional status (Katz ADL score).

Subject Evaluation

- Evaluation of RSV disease-related signs and symptoms and additional questions about health and functioning.
- HRQoL (EQ-5D-5L).

